### 1.2. Secondary Objectives

- 1. For phase 1 portion of the study:
  - a. To determine response rates of the combinations of crenolanib with standard salvage chemotherapy or with 5-azacitidine among patients with refractory/relapsed AML or high-risk MDS with activating FLT3 mutations
  - b. To determine the duration of response in patients with refractory/relapsed AML or high-risk MDS with activating FLT3 mutations treated with crenolanib + standard salvage chemotherapy (arm 1) or crenolanib + 5-azacytidine (arm 2).
  - c. To determine the progression free survival and overall survival of patients with refractory/relapsed AML or high-risk MDS with activating FLT3 mutations treated with crenolanib + standard salvage chemotherapy (arm 1) or crenolanib + 5-azacytidine (arm 2)
  - d. To characterize the pharmacokinetics of crenolanib when combined with standard salvage chemotherapy or with 5-azacitidine in adult patients with refractory/relapsed AML patients with AML or high-risk MDS, and relate crenolanib exposure to outcome (e.g., toxicity and/or FLT3 inhibition).
  - e. To analyze phospho-FLT3 and other pharmacodynamic markers from serially collected circulating leukemic blasts and/or marrow blast samples after treatment with crenolanib-based combinations and correlate with response to therapy.
- 2. For the phase 2 portion of the study:
  - a. To determine safety of the combinations of crenolanib with standard salvage chemotherapy or with 5-azacitidine among patients with refractory/relapsed AML or high-risk MDS with activating FLT3 mutations.
  - b. To determine the duration of response in patients with refractory/relapsed AML or high-risk MDS with activating FLT3 mutations treated with crenolanib + standard salvage chemotherapy (arm 1) or crenolanib with 5-azacytidine (arm 2).
  - c. To determine the progression free survival and overall survival in patients with refractory/relapsed AML or high-risk MDS with activating FLT3 mutations

- treated with crenolanib + standard salvage chemotherapy (arm 1) or crenolanib with 5-azacytidine (arm 2).
- d. To characterize the pharmacokinetics of crenolanib when combined with standard salvage chemotherapy or with 5-azacitidine in adult patients with refractory/relapsed AML and relate crenolanib exposure to outcome (e.g., toxicity and/or FLT3 inhibition).

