#### 5.2.1.2. Remission Consolidation

#### **ARM 1 Consolidation Dosing Schedule:**

- Idarubicin 8 mg/m^2 IV over 1 hr daily on Days 1-2
- Cytarabine 0.75 g/m^2 IV continuously over 90 min on Days 1-3
- Crenolanib will be given Day 5 (+3 day window) continuously until 72 hours prior to next consolidation cycle. If patient remains in CR/CRi/CRp and will proceed to maintenance, crenolanib does not need to be held 72 hours prior to starting first cycle of maintenance.

Consolidation cycles can be a minimum of 28 days or a maximum of 60 days (extending a cycle for more than 60 days would require a conversation with the sponsor). A maximum of 6 consolidation cycles may be given.

A patient must maintain CR/CRi/CRp to be eligible for a second cycle of consolidation. If a patient is in a CR/CRi/CRp at any time, he/she is eligible for maintenance therapy with crenolanib (per physician's discretion). If a patient is to receive transplant, he/she must be discontinued from study treatment prior to transplant.

If at any time during consolidation a patient relapses or is taken off study for any other reason (such as transplant), an end of treatment visit is strongly recommended. This visit will occur within 30 days of discontinuing crenolanib and prior to new treatment regimen or transplant. At the end of the study, patient's survival status will be assessed.

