5.2.1.3. Crenolanib Maintenance

#### **ARM 1 Maintenance Dosing Schedule:**

Patients achieving a remission following induction cycles or patients remaining in remission after consolidation therapy may receive crenolanib for maintenance therapy for up to 365 days. Maintenance therapy will be with single-agent crenolanib and cycles will be defined as 28 days.

If a patient is to receive transplant, he/she must be discontinued from study treatment prior to transplant. If at any time during maintenance a patient relapses or is taken off study for any other reason (such as transplant), an end of treatment visit is strongly recommended. This visit will occur within 30 days of discontinuing crenolanib and prior to new treatment regimen or transplant. At the end of the study, patient's survival status will be assessed.

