#### 5.5. Duration of Therapy

Treatment may continue until one of the following criteria applies:

- 1. Clinically significant progressive disease
- 2. Intercurrent illness that in the opinion of the investigator prevents further administration of treatment
- 3. Patient request
- 4. General or specific changes in the patient's condition render the patient unacceptable for further treatment in the judgment of the investigator
- 5. Unacceptable toxicity that in the opinion of the investigator makes it unsafe to continue therapy
- 6. Treatment interruption due to toxicity that has not recovered to at least grade 1 within 8 weeks
- 7. Patient is to receive HSCT

It is planned that up to 365 days of crenolanib maintenance therapy may be administered for patients deriving benefit from this regimen. This will be administered per physician's discretion or upon any of the criteria mentioned above for treatment discontinuation.

A minimum of 1 full course (defined as the administration of chemotherapy followed by crenolanib for a minimum of 28 days or at the time of protocol specified "pre-cycle 2" bone marrow) will be required for a patient to be considered as having received an adequate trial to evaluate efficacy. Patients who do not complete one cycle of crenolanib therapy will be replaced unless the reason is development of toxicity or progressive disease. All patients receiving at least one dose of study drug will be considered evaluable for toxicity.

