- Bone marrow aspirate within the 28 days preceding study enrollment. Cytogenetics will be obtained prior to therapy (results from prior analysis can be used for this purpose, if done within 6 months). Bone marrow assessments on study will be done per institutional SOC.
  - Adverse events are to be assessed at each visit and recorded in the source records and appropriately reported in the EDC. n.
- Induction 2 will be allowed (per physician's discretion) if patient does not achieve a CR or CRp and cannot proceed to consolidation or maintenance. o.
- This visit will only take place following induction if patient does not continue to consolidation or maintenance. This visit is strongly recommended, all measures should be taken to ensure this visit occurs. An End of Treatment visit should be performed within 30 days post last dose of crenolanib (prior to initiation of new treatment regimen or HSCT). This visit will include physical exams, vitals, ECOG PS, weight, CBC and CMPs; concomitant medications and adverse events should also be assessed. This visit will also require a whole blood sample to be drawn for biomarker and genetic
- An End of Study assessment will be performed for all patients to record overall survival. (This assessment will occur upon the completion of the study) ġ

		Arm 1: Consolic	dation (maximum 6 c	Arm 1: Consolidation (maximum 6 consolidations allowed)		
Procedure	J.	Consolidation 1 (Minimum of 28 days		Consolidation 2-N' (Minimum of 28 days	End of Treatment j (within 30 days post last dose of	End of Study *
	Day 1	Maxillulli uulatioli ol oo uays) Dav 5	Every other week*	Maximum unaudii oi oo days)  Day 1	crenolanib)	
Concomitant medications a	×		X	X	X	
Physical examination b	×			×	X	
Vitals, ECOG PS, Weight, Height c	x			X	x	
Hematology d	x		X	X	X	
Blood chemistries e	×		X	X	X	
PK analysis f		X				
Bone marrow aspiration g			$_{S}$ X			
Adverse events h	x		X	X	X	
Blood for biomarker and genetic testing					×	
Survival follow-up						X

- \* Procedures and assessments to be performed every other week until end of cycle (cycle length cannot exceed 60 days)
- Concomitant medications are to be recorded in the source records and appropriately reported in the EDC at visit.

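### PFS and duration of response are secondary objectives, but no relapse dates are scheduled for collection after the End of Treatment visit

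*Combined protocol and SAP*

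**What the plan says.** Section 1.2 sets two time-to-event objectives that depend on the date of relapse or progression, in both phases and both arms. One is "To determine the duration of response in patients with refractory/relapsed AML or high-risk MDS with activating FLT3 mutations". The other is PFS, listed with overall survival: "To determine the progression free survival and overall survival of patients" for phase 1, and "To determine the progression free survival and overall survival in patients with refractory/relapsed AML or high-risk MDS with activating FLT3 mutations" for phase 2.

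Transplant ends study treatment. Section 5.2.1.2 (consolidation) says: "If a patient is to receive transplant, he/she must be discontinued from study treatment prior to transplant". The induction, maintenance and Arm 2 texts say the same, and Section 5.5 lists "Patient is to receive HSCT" among its stopping criteria.

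The End of Treatment visit comes next. Section 5.2.1.3 says: "This visit will occur within 30 days of discontinuing crenolanib and prior to new treatment regimen or transplant". The keys in Section 9 recommend the visit without making it mandatory. They list examination, vital signs, performance status, weight, blood counts, chemistry, concomitant medication, adverse events and a blood sample for biomarkers. No marrow or response assessment is listed.

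After that visit, the schedules of both arms have one remaining column, End of Study, with survival follow-up as the only marked item. The key reads "An End of Study assessment will be performed for all patients to record overall survival", once, when the study completes. Section 5.2.1.2 agrees: "At the end of the study, patient's survival status will be assessed".

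**The concern.** Duration of response runs from response to relapse. A patient who stops treatment in remission has no scheduled source for the second date once the End of Treatment visit is over. The same holds for the relapse component of PFS.

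The patients affected are not a random subset. Transplant is the reason for stopping most clearly tied to response: in Arm 1, consolidation and maintenance are open only to patients who have reached CR, CRi or CRp, so those who leave these phases for transplant have already responded. Follow-up that ends for a reason linked to prognosis can bias a Kaplan-Meier estimate, and the estimate cannot be checked if later relapse dates do not exist. Durability also matters to the rationale, since Section 2.5 puts forward sustained response as a reason for the azacitidine combination.

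**Working it through.** **Step 1. What is scheduled, by period (Sections 5.2, 5.5 and 9).**

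| Period | Efficacy information scheduled |
|---|---|
| On treatment | Blood counts at visits; marrow by local standard of care; progression is a reason to stop |
| End of Treatment visit | Blood counts; no marrow listed |
| After that visit | Survival status, once, at study completion |

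Relapse on treatment can be dated. Relapse after the End of Treatment visit has no scheduled source. Because that visit lists no marrow, the last marrow-confirmed remission may be earlier than the visit.

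**Step 2. Could another section fill the gap?**
- Section 6.1 keeps a patient under follow-up for outcomes after withdrawal, but only when no suitable crenolanib dose can be found. It gives no schedule and no data items.
- Section 11.2 requires reporting of treatment-related serious events beyond 30 days, and Section 13.2 mentions monitoring after treatment. Both concern safety.
- Sections 5.3.2 and 12.2 capture and summarise the reason for stopping. This shows that a patient left for transplant, but not when relapse followed.
- Section 10 writes out no relapse criterion for AML; it refers to a published standard.
- Section 12 mentions neither PFS nor duration of response: no event, censoring rule or handling of transplant.

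None of these supplies a relapse date after treatment.

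**Step 3. The plan's own design figure.** No precision or power is stated for PFS or duration of response. The one stated figure is 79% power for response (Sections 12.1 and 12.4), with n = 32, p0 = 0.10, p1 = 0.25 and two-sided 10%. Using a one-sample normal approximation:

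power = Φ[(p1 − p0 − 1.645·√(p0(1−p0)/n)) / √(p1(1−p1)/n)]
= Φ[(0.15 − 1.645 × 0.0530) / 0.0765] = Φ(0.82) = 0.794.

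The 79% reproduces, and this point does not touch it. The same inputs give the expected number of responders: 32 × 0.25 = 8 per arm.

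**Step 4. Illustrative scale.** Section 2.4.2 reports 5 patients bridged to transplant in the single-agent studies, against 1 CR, 8 CRi, 7 PR and 11 blast responses. It does not say that the five were responders; that is assumed here.

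| Responders counted | Share transplanted | Of 8 responders per arm |
|---|---|---|
| All 27 responses | 5/27 = 19% | 1.5 |
| 16 CR/CRi/PR | 5/16 = 31% | 2.5 |
| 9 CR/CRi | 5/9 = 56% | 4.4 |

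The 11% printed beside the five patients fits neither 5/49 = 10.2% nor 5/51 = 9.8%; it would need a denominator of about 45 or 46. The counts are used here, not that percentage.

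**Step 5. Would relapse usually come after transplant?** Assume exponential response times with median m months and transplant t months after response. The share still in response at transplant is exp(−t·ln2/m). With m = 3, t = 3 it is 50%; with m = 12, t = 1 it is 94%. The documents give neither m nor t. Over that range, at least half of transplanted responders would still be in response at transplant, so any later relapse would go unrecorded.

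**The case against.** A reader might infer that the plan censors PFS and duration of response when treatment stops. It does not say so. The cut-off follows from what is collected, and it is approximate, because the End of Treatment visit may fall up to 30 days after the last dose. Deaths are still recorded for every patient at study end. If PFS counts death as an event, which the plan leaves open, deaths after transplant can enter it. What goes missing is the relapse date.

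A reader might also infer that transplant goes unrecorded. That is too strong: the reason for stopping is captured, transplant is a listed reason, and the End of Treatment visit is placed before it. The fact of transplant and its rough timing are recoverable, though no exact date is specified.

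Nor do the documents show that transplanted responders make up most of those affected. Patients who stop without relapse for toxicity, on request or after 365 days of maintenance have the same gap, and no figure ranks these reasons.

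The numerical illustration is weak. It comes from single-agent treatment after a median of 3 prior therapies. The 31% must not be read as a ceiling, since the denominator alone moves the share between 19% and 56%.

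Finally, it might be said that the objective cannot be met at all. That goes too far. These are secondary objectives with no stated power, relapse on treatment is observed, and sites could abstract later relapse dates although the protocol does not require it. All of this narrows the point. None of it supplies relapse dates after treatment.

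**Conclusion.** The point holds as a gap in data collection. Followed as written, the schedule yields no relapse or progression date, and no exact transplant or new-therapy date, after the End of Treatment visit for any patient who stops without relapse, in either arm. The loss falls mainly on duration of response and on the relapse component of PFS. Overall survival and the primary response endpoint are not affected.

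The illustrative size, about 1.5 to 4.4 of 8 responders per arm, counts transplant only. It rests on three assumptions: the 25% target response rate is met, all five earlier transplanted patients were responders, and transplant is about as frequent among responders here as in the single-agent studies. Other reasons for stopping would add to it. Neither the direction nor the size of the resulting bias can be derived from the documents.

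This should be corrected, because the missing dates cannot be replaced by any choice of analysis.

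**What to change.** 1. At the End of Study contact, with chart abstraction, record for every patient, whatever the reason for stopping: date of relapse or progression, date of transplant, date of first new anti-leukemic therapy, and date of death or last known alive. The last is arguably already implied by recording overall survival.
2. Reconcile Section 9 with the Section 6.1 sentence on follow-up for outcomes, so that one rule covers all patients off treatment.
3. In Section 12, define the PFS and duration-of-response events (including whether death counts), the start dates and the censoring rules.
4. Report Kaplan-Meier estimates both with and without censoring at transplant. The sponsor should prespecify which is the main one. That choice depends on the question asked, and the dates in item 1 are needed to show both.

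The cost is a few date fields on a contact already planned and some chart work. Treatment, visits, sample size and the primary analysis stay as they are. The limitation is that relapse dates gathered retrospectively from standard-of-care assessments will be less exact than dates from scheduled assessments.

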#### 6. DOSING MANAGEMENT

#### 6.1. Dosing Levels

Toxicities will be graded using the NCI CTCAE, Version 4.03 (Appendix IV).

- Dose reductions for non-hematologic toxicities due to crenolanib, will be done according to the schema outlined in Tables 6.1 and 6.2
- Reductions below 60mg BID are not planned; dose reductions beyond those mentioned in Table

6.2 or different than those specified, should be discussed with the PI and the sponsor and documentation of the justification recorded. If an appropriated dose is not identified, then it will lead to patients' withdrawal from the study drug, in which the patient will stop taking crenolanib, but will still be followed for outcomes.

Table 6.1 Crenolanib dose reduction for All Toxicities related to study drug

Toxicity (NCI Criteria)	Dose Modification
Grade 1 or 2	No dose modification
Clinically significant persistent grade 2 despite optimal therapy	May hold drug until toxicity resolves to grade 1 or less. Restart drug at same dose level (Table 6.2).
Grade 3 or 4	Hold drug until toxicity resolves to grade 1 or less. Restart drug at next lower dose level (Table 6.2).

Table 6.2 Crenolanib dose reduction schedule

Dose Level	Crenolanib Dosing
0	60 mg BID
1 (starting dose)	60 mg TID
2	80 mg TID
3	100 mg TID

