### 6.2. Dose Reductions of Crenolanib for Hematologic Toxicities

Patients with leukemia usually present with abnormal peripheral blood counts at the time therapy is started and myelosuppression is an expected event during the course of therapy for acute leukemia. Thus, no dose adjustments or treatment interruptions for myelosuppression will be planned for the first 4 weeks of therapy. After this time, treatment interruptions and dose adjustments may be considered according to the following guidelines:

The following guidelines can be used for these patients:

- Patients with a response (i.e., no residual leukemia) and pre-cycle counts of neutrophils  $>1x10^9/L$  and platelets  $>100 x10^9/L$  who have sustained low counts of neutrophils  $<0.5 x10^9/L$  or platelet counts  $<25 x x10^9/L$  for more than 4 consecutive weeks in the current cycle, may receive a subsequent course at 1 dose level reduction. A reduction of 2 dose levels may be considered if the myelosuppression was deemed severe and life threatening by the treating physician, and if it is in the patient's best interest.
- If there are persistent peripheral blood blasts, or the bone marrow shows >5% blasts, may continue treatment regardless of neutrophil and platelet count and give supportive care as needed.
- If no marrow evidence of leukemia, consider holding therapy until recovery of granulocytes to  $\ge 1 \text{ x} 10^9/\text{L}$  and platelets  $\ge 60 \text{ x} 10^9/\text{L}$ , then resume at same or 1 lower dose level according to guidelines mentioned in Table 6.2.
- For prolonged myelosuppression, defined as delayed recovery of ANC to  $\ge 1 \times 10^9$ /L, platelets to  $\ge 50 \times 10^9$ /L beyond 6 weeks, crenolanib will be withheld. Resume crenolanib at a lower dose level after ANC  $\ge 1 \times 10^9$ /L, platelets to  $\ge 50 \times 10^9$ /L. Discontinue crenolanib treatment upon a 2nd episode of myelosuppression.

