- Complete physical examination should be performed on day 1 of each cycle. If patient discontinues drug and does not proceed to maintenance, an End of Treatment visit is strongly recommended with a physical examination. Physical exams that are performed as per institutional standard of care will also be collected upon sponsor's request to assess safety.
- Weight, PS and vital signs (temperature, blood pressure, pulse & respiratory rate) should be collected at each scheduled visit for physical examination. (For times of physical examination refer to
- description under b) Height will only be captured at screening. Hematology assessments include complete blood count with differential and platelet count. Hematology labs should be drawn at screening and during consolidation 1 on day 1 and every other week until end of cycle. If patient continues to consolidation 2 (or beyond), hematology labs will be required on day 1. If patient discontinues drug and does not proceed to maintenance, an End of Treatment visit is strongly recommended with hematology labs. Labs should be drawn per study schedule; however, routine labs will that are be drawn as per institutional standard of care will also be collected upon sponsor's request to assess safety. (Local labs will be accepted, these labs must be sent to the central site)
- Chemistry assessments include glucose, bicarbonate, protein, serum creatinine, creatinine clearance, sodium, potassium, calcium, blood urea nitrogen (BUN), albumin, total bilirubin, alkaline phosphatase, AST, ALT and LDH. Chemistry labs should be drawn during consolidation 1 on day 1 and every other week until end of cycle. If patient continues to consolidation 2 (or beyond), chemistry labs will be required on day 1. If patient discontinues drug and does not proceed to maintenance, an End of Treatment visit is strongly recommended with chemistry labs. Labs should be drawn per study schedule; however, routine labs that are drawn as per institutional standard of care will also be collected upon sponsor's request to assess safety. (Local labs will be accepted, these labs must be sent to the central site)
  - Peripheral blood will be drawn to assess PK at these time points at day 5 (of consolidation) (depending on when patient starts crenolanib, this should be first day of crenolanib administration) predose and post-dose at 2 hours ( $\pm$  15 minutes), 4 hours ( $\pm$ 30 minutes), and 8 hours ( $\pm$ 2 hours).

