    - Bone marrow assessments on study will be done per institutional SOC.
    - Adverse events are to be assessed at each visit and recorded in the source records and appropriately reported in the EDC. ಹ. .. ...
- Subsequent consolidation cycleswill be allowed per physician's discretion. Up to 6 cycles of consolidation will be allowed.
- This visit will only take place following induction if patient does not continue to maintenance. This visit is strongly recommended, all measures should be taken to ensure this visit occurs. An End of Treatment visit should be performed within 30 days post last dose of crenolanib (prior to initiation of new treatment regimen or HSCT). This visit will include physical exams, vitals, ECOG PS, weight, CBC and CMPs, concomitant medications and adverse events should also be assessed. This visit will also require a whole blood sample to be drawn for biomarker and genetic testing.
  - An End of Study assessment will be performed for all patients to record overall survival. (This assessment will occur upon the completion of the study)

	Arm 1: Maintenance (max	Arm 1: Maintenance (maximum 365 days of crenolanib allowed)	(p)
Procedure	Maintenance Day 1 of Cycle N (1 cycle is 28 days)	End of Treatment ' (within 30 days post last dose of crenolanib)	End of Study j
Concomitant medications a	×	×	
Physical examination b	×	Х	
Vitals, ECOG PS, Weight, Height c	×	Х	
Hematology d	X	Х	
Blood chemistries e	×	Х	
Bone marrow aspiration f	$f^{\mathbf{X}}$		
Blood for biomarker and genetic testing		Х	
Adverse events g	X	X	
Crenolanib administration h	X		
Survival follow-up			X

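### No mandated laboratory check inside Arm 1 consolidations 2 to 6 falls on crenolanib, so laboratory toxicity in later cycles may be under-ascertained

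*Combined protocol and SAP*

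**What the plan says.** Section 9, Arm 1 Consolidation schedule and key:

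- In the first consolidation, hematology and chemistry are due "during consolidation 1 on day 1 and every other week until end of cycle".
- From the second consolidation on, the key says of hematology: "If patient continues to consolidation 2 (or beyond), hematology labs will be required on day 1". Of chemistry it says: "If patient continues to consolidation 2 (or beyond), chemistry labs will be required on day 1".
- The table gives Consolidation 2-N a single column, Day 1, which also carries concomitant medications and adverse events. The key adds: "Adverse events are to be assessed at each visit and recorded in the source records".
- Labs drawn as local standard care are also collected, but only if the sponsor requests them. No frequency is given.

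Section 5.2.1.2 (Remission Consolidation) sets the dosing window: "Crenolanib will be given Day 5 (+3 day window) continuously until 72 hours prior to next consolidation cycle". If the patient goes on to maintenance instead, "crenolanib does not need to be held 72 hours prior to starting first cycle of maintenance". Cycles last 28 to 60 days, and at most six are allowed.

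Three other provisions depend on what is measured within a cycle:

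- Table 6.1 (Section 6.1) directs the site to "hold drug until toxicity resolves to grade 1 or less" for a grade 3 or 4 toxicity.
- Section 6.2 says that responders with adequate pre-cycle counts whose counts then stay low "for more than 4 consecutive weeks in the current cycle, may receive a subsequent course at 1 dose level reduction". It also withholds crenolanib when count recovery is delayed beyond 6 weeks.
- Section 11.1.2 asks for the highest or lowest abnormal chemistry value of each course on the case report form. It excludes abnormal hematologic values from that form.

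**The concern.** Several phases have sparse visits, but only Arm 1 Consolidation 2-N combines Day-1-only checks with a required drug break just before the visit. Induction 2 and Consolidation 1 have checks every other week. Arm 2 from cycle 3 and maintenance in both arms are also Day 1 only, but crenolanib is continuous there, so Day 1 reflects current exposure.

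The provisions in Sections 6.2 and 11.1.2 presuppose several values within a course, and the schedule supplies one, before crenolanib starts. A symptomless grade 3 or 4 laboratory abnormality during dosing comes to light only if someone happens to draw blood. Section 2.4.2 reports transaminase elevations in 8 to 11% of patients on single-agent crenolanib.

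Two later uses of the data are exposed. The phase II toxicity boundary in Section 12.1 counts grade 3 or 4 non-hematologic toxicity with no stated cycle limit, so events that are never measured lower the count. Section 5.1 allows the MTD to be refined on delayed or cumulative toxicity, and it wants a recommended dose that is deliverable over multiple cycles. Later consolidations are part of that evidence in Arm 1.

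**Working it through.** The plan states no figure for on-drug time or for the number of on-drug checks, so there is none to reproduce. The check is calendar arithmetic.

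**Inputs**

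- Cycle length L: 28 to 60 days (Section 5.2.1.2). Section 5.3.2 gives 4 to 6 week intervals between courses in responders, so L = 42 is also shown.
- Crenolanib start day s: 5 to 8 (Day 5 with a +3 day window).
- Stop: 72 hours, or 3 days, before the next Day 1. The next Day 1 is day L + 1.
- Mandated checks in Consolidation 2-N: Day 1.
- Consolidation 1 pattern, for comparison: Day 1 plus every other week, taken as Days 15, 29, 43 and 57. These days are my assumption, since the plan does not name them.

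**On-drug days per cycle** = (L + 1 − 3) − s = L − 2 − s

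| Cycle length | s = 5 | s = 8 | Mandated on-drug checks, Consolidation 2-N | On-drug checks under the Consolidation 1 pattern |
|---|---|---|---|---|
| 28 days | 26 − 5 = 21 | 26 − 8 = 18 | 0 | 1 (Day 15) |
| 42 days | 40 − 5 = 35 | 40 − 8 = 32 | 0 | 2 (Days 15, 29) |
| 60 days | 58 − 5 = 53 | 58 − 8 = 50 | 0 | 4 (Days 15, 29, 43, 57) |

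The zero holds for every L, because Day 1 is earlier than s = 5.

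**Across cycles.** In a patient who receives all six consolidations, the second to fifth are each followed by another consolidation and so by the 72-hour break. Four such cycles give:

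- 28 days: 4 × 18 = 72 to 4 × 21 = 84 days on drug
- 42 days: 4 × 32 = 128 to 4 × 35 = 140 days
- 60 days: 4 × 50 = 200 to 4 × 53 = 212 days

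The last consolidation is different. If it leads to maintenance without a hold, on-drug time up to maintenance Day 1 is L + 1 − s: 21 to 24, 35 to 38 or 53 to 56 days. The check on that day can fall on drug. Otherwise an End of Treatment visit is strongly recommended within 30 days of the last dose.

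**Rules against scheduled data**

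- *Low counts for more than 4 consecutive weeks (Section 6.2).* The rule requires adequate pre-cycle counts, so Day 1 of the cycle is its baseline. No other scheduled count exists in that cycle, and a single count at the next Day 1 cannot show duration.
- *Recovery delayed beyond 6 weeks (Section 6.2).* In a cycle longer than 6 weeks, no count is scheduled at that point.
- *Grade 3 or 4 (Table 6.1).* Any result can trigger the rule, but no mandated draw exists while the drug is being taken.
- *Chemistry extreme per course (Section 11.1.2).* Scheduled draws give one value per course, taken before crenolanib starts.

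**The case against.** The strongest reply is that the schedule is a floor and the plan has other routes to the same information. Much of that stands.

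- A reader might infer that the hold and reduction rules cannot be applied in these cycles. The documents do not support this. Table 6.1 acts on grade, whatever the source of the result. Section 6.2 is largely permissive, and its 4-week rule concerns a later course. Section 5.3.2 makes the next course in responders conditional on count recovery.
- A reader might infer that on-drug adverse events are lost. They need not be. Section 11 captures any new event after study drug starts. The Appendix II diary has a side-effect column for each dosing day. Section 11.2 captures serious events from consent to 30 days after the last dose, and Section 13.2 provides continuous monitoring and biweekly calls. A Day 1 assessment may also look back over the preceding cycle.
- A reader might infer that ALT or counts recover during the 72-hour break and so look normal on Day 1. No section gives a recovery time, so this cannot be claimed.
- A reader might take 60-day cycles as typical. That length is a ceiling, and Section 5.3.2 points to 4 to 6 weeks.
- The DLT period is cycle 1 with weekly labs, and the primary response endpoint is untouched. Induction 2, Consolidation 1 and maintenance also supply multi-cycle tolerability data. Tapering of visits may be deliberate.
- Hematologic values are excluded from the case report form, so sparse draws do not by themselves cost that form any hematology data.

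The laboratory gap remains. A diary cannot record ALT or platelets, and continuous monitoring sees only what has been measured and sent. The standard-care labs that would fill the gap have no stated frequency and enter the data only on request.

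**Conclusion.** The point holds for mandated laboratory checks. Inside Arm 1 consolidations 2 to 6 there are none on crenolanib, against about 18 to 21 days of dosing per 28-day cycle, 32 to 35 per 6-week cycle and 50 to 53 at the 60-day ceiling. The count-duration rules, the detection of symptomless laboratory toxicity and the per-course chemistry extreme therefore rest on local practice that the plan neither specifies nor routinely collects. Laboratory toxicity in later cycles may be under-ascertained. By how much cannot be calculated, because the documents give neither the frequency of local draws nor a rate of laboratory toxicity in later consolidations.

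This rests on the 72-hour break and the visit days being followed as written. The laboratory timing is stated in words in the key, so it does not depend on the broken table. The adverse event timing rests on the table together with the statement that events are assessed at each visit. The point is worth correcting, but it does not threaten the primary endpoint or the DLT assessment.

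**What to change.** Reconcile Sections 5.2.1.2, 6.1, 6.2, 9 and 11.1.2, so that the assessments match the rules and the reporting that depend on them.

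- *Minimum change.* Make local chemistry and hematology results obtained during crenolanib dosing in Consolidation 2-N required study data, instead of collecting them on sponsor request. Section 11.1.2 then needs a matching sentence for hematology, since it now keeps abnormal hematologic values off the case report form. Local labs are already accepted, so the cost is data entry.
- *Optional change.* If the sponsor chooses to align the assessment schedule, the existing Consolidation 1 every-other-week column could be extended to Consolidation 2-N. That means one table column and the two lab entries in the key. On the day pattern assumed above, it gives one on-drug check in a 28-day cycle, two in a 6-week cycle and four in a 60-day cycle. The added cost is some routine draws where local care does not already cover them.

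No dose, hold or stopping rule is proposed.
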